13. STATISTICAL CONSIDERATIONS

13.1 Study Design, Sample Size Considerations and Accrual Rate

13.1.1 Study Design

A single-arm, Phase II trial will be employed to obtain initial assessment of the effect of HCQ in modulation of PAR4 levels among patients with oligometastatic prostate cancer treated with surgery or radiation. The primary endpoint is based on obtaining a 50% increase in PAR-4 levels from baseline within the 3-month period of HCQ administration.

13.1.2 Sample size justification

Based on an ongoing Phase I trial of HCQ, we will assume that the proportion of patients who will exhibit a 50% induction in PAR-4 from baseline levels is equal to 0.50 compared to a null hypothesis of 0.20. A sample of 18 patients will provide 84% power to detect this hypothesized difference in proportion based on a two-sided test with 5% significance level. Assuming no more than a 10% drop out rate, we will enroll a total of 20 patients into the study. No patients dropped out of our Phase 1 study, which ascertained 200 mg daily as the optimal biological dose.²⁵

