
11. MEASUREMENT OF HCQ EFFECT

11.1 PRIMARY OBJECTIVE

To assess the effect of HCQ on PAR-4, first compliance with HCQ planned dose regimen should be ascertained.

HCQ regimen compliance: pill diaries (Appendix D) and/or patient-reported HCQ compliance will be evaluated to assess participant adherence to HCQ daily regimen at follow-up clinic visits with study staff. Additionally, study staff may institute a telephone check with study participants on a PRN basis, should compliance to the HCQ regimen need to be monitored outside regular clinic visit schedule.

Participants who completed 80% of the planned HCQ doses will be considered evaluable for the Primary Endpoint, PAR-4 increase.

PAR-4 level will be assessed for each participant at the following timepoints:

- Enrollment/Baseline visit
- Day 14 post- HCQ initiation
- Day 30 of HCQ
- Day 60 of HCQ
- Day 90 of HCQ
- 6-month follow-up (during a standard of care visit)
- 12-month follow-up (during a standard of care visit)

It is expected that HCQ will induce an elevation of PAR-4 expression among 50% of the participants within the 90-day administration of HCQ. The elevation is expected to be a 50% increase from baseline PAR-4 levels among half of the study participants.

11.2 SECONDARY OBJECTIVES:

11.2.1 HCQ safety analysis and Treatment Toxicity: frequency and incidence tables of toxicity and AEs will be generated. Toxicity will be assessed using Common Terminology Criteria for Adverse Events V5.0 (for HCQ and for radiation therapy), as well as the Clavien-Dindo classification of surgical complications in the case of patients who underwent surgery (Appendix F). All patients will be evaluable for toxicity (HCQ) from the time of their first treatment with Hydroxychloroquine.

11.2.2 HCQ immunologic effect on PAR-4 Levels: as measured by serum (or plasma) blood collected at multiple timepoints. PAR-4 secretion is expected to come primarily from normal cells of the patient. The contribution of the tumor cells to serum levels of PAR-4 is expected to be minimal, but this has not been directly tested. Association between PAR-4 levels and clinical stage will be assessed.

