13.3 Analysis of Primary and Secondary Endpoints

To be considered “evaluable” a patient must have completed 80% of the 90-day planned dose of HCQ.

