13.3.1 PAR-4 Levels

Patient compliance with planned HCQ regimen will be assessed by the treating physician and the patient-reported pill diary will be reviewed. For each evaluable patient, descriptive statistics will be calculated to summarize PAR-4 levels at each time point of follow-up. Percent change from baseline PAR-4 compared to each follow-up time point will likewise be calculated. The proportion of patients who exhibit a 50% induction in PAR-4 compared to baseline within the 3-month therapy period will be calculated and a one-sample test for proportion will be performed.

Secondary analyses of the primary endpoint will also be performed. Continuous changes in PAR-4 levels will also be assessed using paired t-test or nonparametric analog. Linear mixed models will also be employed to analyze repeatedly measured levels of PAR-4 and association with clinical parameters as well as PSA levels. Other secondary analyses will include summary of the PAR-4 induction profile over the 3-month treatment period and after end of therapy period.

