The study statistician and staff from the Biostatistics and Bioinformatics Shared Resource (BB SRF) of the Markey Cancer Center (MCC) will work closely with the study team, the Clinical Research Office (CRO) at MCC and the Cancer Research Informatics (CRI) Shared Resource at MCC to develop the Data Management Plan (DMP) for this trial. The DMP will provide details for development of eCRFs in the OnCore system, trial-specific processes for data entry, generation of reports, data management and statistical analysis. Specifically, the statistician will attend several meetings including the eCRF development meeting, Data Management and Development meeting and the Protocol Initiation meeting. Appropriate and accurate collection of primary and secondary study endpoints and inclusion of valid values and range checks for data fields will be designed for the eCRFs. The OnCore clinical trial management system, managed by Markey's CRO and CRI, will be the primary database repository of clinical data from all patients enrolled into this trial. Furthermore, the CRI at MCC has established workflows for receipt, storage and secure access of high-throughput bioinformatics data (next generation sequencing) using the university's high performance computing facility. The study statistician and [name] from the BB SRF have access to both OnCore clinical databases and bioinformatics data. Data will be accessed by the study statistician on a regularly-scheduled basis as defined in the DMP to perform statistical programming for conduct of data quality control, data management, generation of interim reports and statistical analysis. In collaboration with the study team, procedures will be developed for timelines for data quality control, resolution of data queries, interim safety reporting and final data analysis.

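### At 18 evaluable patients no success count gives 84% power at a true two-sided 5% level (exact test: 76.0%), and the one-sample test, which decides results such as 7/17 or 7/18, is not named

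*Combined protocol and SAP*

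**What the plan says.** Section 13.1.2 assumes that the PAR-4 response proportion "is equal to 0.50 compared to a null hypothesis of 0.20". It then states: "A sample of 18 patients will provide 84% power to detect this hypothesized difference in proportion based on a two-sided test", with a 5% significance level. To allow for at most 10% dropout, "we will enroll a total of 20 patients into the study".

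Section 13.3.1 describes the primary analysis only in these terms: "a one-sample test for proportion will be performed". Neither section says whether the test is exact, an uncorrected z-test, continuity-corrected or something else. Neither gives the number of responders that counts as success.

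The number analysed is not fixed at 18. Under Section 13.3, "a patient must have completed 80% of the 90-day planned dose of HCQ" to be evaluable, and Section 11.1 applies the same 80% rule to the primary endpoint. Section 13.4 says the Data Management Plan will cover "trial-specific processes for data entry, generation of reports, data management and statistical analysis". That plan is not among the documents, so the test is unnamed in what is in hand.

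**The concern.** With 18 patients and a null rate of 0.20, the expected null count is 3.6, and the attainable error rates move in large steps. A smooth normal-approximation power need not match any rule that can be applied to an integer count. Two things are at stake. First, if the analysis uses an exact test, the chance of missing the hypothesised effect at 18 evaluable is 24%, not the 16% that 13.1.2 implies. Second, some plausible results are significant under one ordinary one-sample test and not under another. A test chosen after the count is known would then be open to challenge.

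**Working it through.** **Inputs.** Section 13.1.2: p0 = 0.20, p1 = 0.50, n = 18, two-sided 5%, 20 enrolled, dropout up to 10%. Section 13.3.1: a one-sample test of a proportion, version not given.

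**Reproducing the 84%.** Uncorrected normal approximation, with the null standard error for the cut-off and the alternative standard error for power:

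Φ[(0.30 × √18 − 1.96 × 0.40) / 0.50] = 0.836.

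The figure is therefore not an arithmetic slip.

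**Exact binomial at n = 18.**

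| Benefit cut-off | Upper tail at 0.20 | With 0/18 added (0.0180) | Power at 0.50 |
|---|---|---|---|
| ≥7 (uncorrected z-test) | 0.0513 | 0.0693 | 0.8811 |
| ≥8 (either exact test) | 0.0163 | 0.0343 | 0.7597 |

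The 0/18 tail is added because both tests in the table also reject there. These cut-offs are adjacent, so nothing lies between 76.0% and 88.1%. The cut-off with power above 84% exceeds 5% on its upper tail alone.

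**Results that turn on the test.** For the z-test at 7/18, z = (7 − 3.6)/√(18 × 0.16) = 2.003. Central exact doubles the upper tail: 2 × 0.0513 = 0.103.

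| Result | z-test | Minimum-likelihood exact | Continuity-corrected z | Central exact |
|---|---|---|---|---|
| 7/18 | 0.045 | 0.069 | 0.087 | 0.103 |
| 7/17 | 0.029 | 0.060 | 0.060 | 0.075 |

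At a true rate of 0.50, exactly 7 responders has probability 0.1214 at n = 18 and 0.1484 at n = 17.

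**Benefit cut-offs by number evaluable.**

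| Test | 15 | 16 | 17 | 18 | 19 | 20 |
|---|---|---|---|---|---|---|
| z-test | 7 | 7 | 7 | 7 | 8 | 8 |
| Minimum-likelihood exact | 7 | 7 | 8 | 8 | 8 | 8 |
| Central exact | 7 | 8 | 8 | 8 | 8 | 9 |

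The z-test and the minimum-likelihood test differ only at 17 and 18. The two exact tests differ from each other at 16 and 20, so the word exact alone does not settle the rule.

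**Averaging over losses.** Assume the number evaluable is Binomial(20, 0.9), with losses independent. Then P(17) = 0.1901 and P(18) = 0.2852, together 47.5%. At a true rate of 0.50, the z-test and minimum-likelihood verdicts differ with probability 0.1901 × 0.1484 + 0.2852 × 0.1214 = 0.063. Weighting power and two-sided size by the same distribution gives:

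| Loss | z-test power / size | Minimum-likelihood power / size |
|---|---|---|
| 5% | 84.9% / 4.7% | 81.7% / 3.9% |
| 10% | 83.7% / 5.3% | 77.4% / 3.5% |
| 15% | 81.4% / 5.2% | 75% / 3.2% |

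**The case against.** The strongest reply is that 84% is a fair description if the z-test matching the formula is intended. Averaged over 20 enrolled with 10% loss, that test has 83.7% power and 5.3% size. The 76% applies only if an exact test is used, which no section says. Ten percent is also a ceiling in 13.1.2, and the same section reports no dropouts in the Phase 1 study. At 19 evaluable the z-test and both exact tests require 8 responders (82.0% power), and at 20 the z-test and minimum-likelihood test agree (86.8%). The 6.9% size includes the 0/18 tail, which nobody would call success; false claims of benefit at ≥7/18 run at 5.13%. The affected results are few: the z-test and minimum-likelihood verdicts differ in 6.3% of trials at a true rate of 0.50 and 1.5% at 0.20. This is also an early single-arm trial with supporting analyses.

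Most of this stands as a limit on size, and it shows that the trial is not grossly mis-sized. It does not rescue the sentence. Section 13.1.2 makes its claim at 18 patients, not as an average over losses, and at 18 the z-test breaches the stated level even without the lower tail. The 80% dosing rule can also cut the evaluable number below what dropout alone implies, and no rate is given for it. The supporting analyses do not decide which p-value is primary. The figures here ignore the interim look in Section 13.2, but so does the plan's own 84%.

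**Conclusion.** The concern holds. At 18 evaluable, 84% power and a two-sided 5% level cannot both be had: the choice is 76.0% power at 3.4% size or 88.1% at 6.9%. The test and its success count are not named in the documents in hand, and that omission decides the primary result at 7/17 and 7/18.

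The figures at fixed n rest only on the plan's 0.20 and 0.50 and on a single-stage analysis. The 6.3% rests also on independent 10% loss from 20 enrolled, and it compares only the z-test with the minimum-likelihood exact test. The Data Management Plan may name the test. If it does, the second gap closes, but the 84% still needs correcting. This should be fixed; it does not by itself call for a larger trial.

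**What to change.** 1. In 13.1.2, replace the power statement with: 18 evaluable patients give 76% power (0.20 against 0.50) with an exact two-sided binomial test at the 5% level.

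2. In 13.3.1, name the version of the exact test and fix the success count by number evaluable before analysis. For the minimum-likelihood test:

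| Evaluable | Success count | Power | Two-sided size |
|---|---|---|---|
| 15 | ≥7 | 69.6% | 1.8% |
| 16 | ≥7 | 77.3% | 2.7% |
| 17 | ≥8 | 68.5% | 3.3% |
| 18 | ≥8 | 76.0% | 3.4% |
| 19 | ≥8 | 82.0% | 3.8% |
| 20 | ≥8 | 86.8% | 4.4% |

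State that 0 responders is not success even where the test rejects. State also that this rule controls total two-sided size, not 2.5% per side: the upper tail is 2.7% at 16 and 3.2% at 20. If 2.5% per side is wanted, name the central exact test instead. It needs ≥8/16 and ≥9/20 (power 59.8% and 74.8%), and its other counts are the same.

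3. If the Data Management Plan already names the test and count, cite it in 13.3.1.

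The cost is wording only, with no extra patients. The price is a less favourable stated power (76% instead of 84% at 18, and 68.5% at 17), and 7/17 and 7/18 will not count as success. Keeping the uncorrected z-test would also require naming it and disclosing its 6.9% size at 18, so it would not honour the stated 5% level.

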13.1.3 Accrual Rate

The accrual rate is estimated to be one patient per month. Based on this enrollment rate, we will complete the accrual of 20 patients in about 18 months.

13.2 Interim Monitoring for Efficacy

We propose to assess the proportion of patients who will exhibit induction levels in PAR-4 after half of the patients have been enrolled into the trial. Bayesian interim monitoring methods using posterior probabilities, credible intervals and predictive probabilities will be calculated based on proportion of patients exhibiting a 50% induction in PAR-4 levels. Briefly, a beta distribution will be assumed for the proportion of PAR-4 response and uninformative and neutral prior distributions will be utilized.

After half of the participants are enrolled on-study (n = 10-11), the proportion of patients with PAR-4 induction will again be estimated and posterior distributions and predictive posterior distributions will be calculated. Accrual will continue during interim analysis. Based on posterior probabilities and credible intervals from the interim analysis, we will then determine whether to continue or stop accrual efforts to attain the planned sample size of 20.

13.3 Analysis of Primary and Secondary Endpoints

To be considered “evaluable” a patient must have completed 80% of the 90-day planned dose of HCQ.

13.3.1 PAR-4 Levels

Patient compliance with planned HCQ regimen will be assessed by the treating physician and the patient-reported pill diary will be reviewed. For each evaluable patient, descriptive statistics will be calculated to summarize PAR-4 levels at each time point of follow-up. Percent change from baseline PAR-4 compared to each follow-up time point will likewise be calculated. The proportion of patients who exhibit a 50% induction in PAR-4 compared to baseline within the 3-month therapy period will be calculated and a one-sample test for proportion will be performed.

Secondary analyses of the primary endpoint will also be performed. Continuous changes in PAR-4 levels will also be assessed using paired t-test or nonparametric analog. Linear mixed models will also be employed to analyze repeatedly measured levels of PAR-4 and association with clinical parameters as well as PSA levels. Other secondary analyses will include summary of the PAR-4 induction profile over the 3-month treatment period and after end of therapy period.

13.3.2 Analysis of Secondary Endpoints

Clinical Endpoints.

Progression-free survival (PFS) will be estimated using the Kaplan-Meier method and estimates of median PFS and PFS rates at specific time points will be calculated.

Likewise, median, 1-year and 3-year ADT-free survival will be estimated using the Kaplan-Meier method.

Exploratory analysis for association of PFS and ADT-free survival with PAR-4 and PSA levels will be assessed using the Cox regression model.

Correlative and QOL endpoints. PSA levels will be assessed according to the schedule described by the study calendar above and PSA doubling time will be calculated. Association of PSA levels with PAR-4 levels will be determined using Spearman or Pearson’s correlation coefficient. Quality of life (QOL) measured by the EORTC QLQ-C30 supplemented with QLQ-PR25 will be evaluated and descriptive statistics of QOL scores will be calculated. Association of QOL with PAR-4, PSA and clinical endpoints will be determined in an exploratory manner using correlations and survival analysis models.

Safety analysis. All patients who received study drug will be included in the safety analysis. Frequency and incidence tables of toxicity and AEs will be generated in the overall patient group. We will generate a safety report for review by the Markey Cancer Center’s Data Safety and Monitoring Committee (DSMC) based on an intent-to-treat population.

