1.2 Secondary Objectives

- Median Progression-Free Survival (time to clinical progression)
- 1- and 3-year Androgen Deprivation Therapy (ADT) Free Survival
- HCQ Treatment toxicity (AEs and SAEs during HCQ administration) and radiation toxicity to be assessed and recorded utilizing the CTCAE v5.0. Surgical Complications will be scored using the Clavien-Dindo Classification (Appendix F).
- Immunological effect of HCQ by analyzing peripheral blood mononuclear cells (PBMCs) at day 0 and Day 30 of treatment, and also, Day 60 (+ 6 weeks) of treatment.
- Quality of life as measured by the EORTC QLQ-C30 + QLQ-PR25

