5.5 Duration of Therapy

In the absence of treatment delays due to adverse event(s), hydroxychloroquine treatment will continue for 3 months or until one of the following criteria applies:

- Disease Progression, assessed by standard of care and defined as either:
 - PSA progression (an increase in PSA > 25% above baseline at study entry), or
 - Symptomatic progression (increasing pain from metastatic lesion), or
 - Progression of baseline-detected lesions (soft-tissue lesions as assessed by RECIST and bone lesions as assessed by the MDA criteria (respectively, Appendix H.1 and Appendix H.2)).
Additionally, CT C/A/P and/or fluciclovine or PSMA PET scans may be performed at the time of either Symptomatic or PSA Progression at discretion of the treating physician.
 - Appearance of new metastatic lesions
- Intercurrent illness that prevents further administration of treatment
- Unacceptable adverse event(s)
- Patient decides to withdraw from the study
- General or specific changes in the patient's condition that render the patient unacceptable for further treatment in the judgment of the investigator

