11.3 Four Types of Disease Progression

1. **PSA or Biochemical Progression:** defined as a PSA increase of $\geq 25\%$ and ≥ 2 ng/mL if PSA was ≥ 2 ng/mL from baseline (OR a PSA increase of $\geq 25\%$ if PSA was < 2 ng/mL at study enrollment).
2. **Symptomatic Progression:** defined as increasing pain from baseline-detected metastatic lesion. Time to first symptomatic event will be calculated from study enrollment until the event of symptoms due to metastatic disease.
3. **Local Progression of baseline-detected lesions depend on site:**
 - 3a. ***soft-tissue metastatic lesion:*** local progression is defined as an increase of $\geq 20\%$ in the largest tumor dimension with a minimum absolute increase of 5 mm. All lesions are considered target lesions, irrespective of size, if they are suspicious on choline PET-CT. See Appendix H.1 for RECIST v1.1.
 - 3b. ***bone metastases:*** local progression is assessed using the MD Anderson Cancer Center-criteria²⁶⁻²⁷, and defined as a $\geq 25\%$ increase in size of a measurable lesion or a $\geq 25\%$ increase in the size of ill-defined lesions on CT considered to be progression. MDA bone-specific response criteria in Appendix H.2.
4. **Distant Progression:** appearance of new metastatic lesions

11.4 Definition of Disease Assessments to evaluate Progression-Free Survival and ADT-Free Survival

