11.4.2 Progression-Free Survival (time to clinical progression)

Four types of progression are defined in 11.3. Progression is calculated from time of study enrollment until progression (per the 4 specified definitions) or death. Events for PFS are:

1. PSA or biochemical progression: defined as a PSA increase of $\geq 25\%$ and ≥ 2 ng/mL (if PSA was ≥ 2 ng/mL from baseline)
2. Symptomatic progression: increasing pain from metastatic lesion
3. Local progression of baseline-detected lesions: each metastasis is a target lesion independently assessed as:
 - soft-tissue lesions assessed per RECIST v1.1 (Appendix H.1)
 - bone lesions assessed per MDA bone-specific response criteria (Appendix H.2)
4. Distant progression: appearance of new metastatic lesions.

If an event is identified, then the time to the event will be recorded as the first instance where any of the above four situations occur.

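### PFS is labelled as clinical progression but a PSA rise alone ends it, and regressing it on PSA is partly circular if the covariate is on-study PSA change, ratio or doubling time

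*Combined protocol and SAP*

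**What the plan says.** Section 1.2 lists the secondary endpoint as "Median Progression-Free Survival (time to clinical progression", and the heading of 11.4.2 repeats the label. The first PFS event in 11.4.2 is "PSA or biochemical progression: defined as a PSA increase of" at least 25% and at least 2 ng/mL, for men with baseline PSA of 2 ng/mL or more. The other events are symptomatic, local and distant progression, and death. The dating rule is that "the time to the event will be recorded as the first instance where any of the above four situations occur". Neither a symptom nor an imaging finding is needed for the PSA event.

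Section 13.3.2 then plans the regression: "Exploratory analysis for association of PFS and ADT-free survival with PAR-4 and PSA levels will be assessed using the Cox regression model". It does not say whether the PSA covariate is baseline, a landmark value, a change or a time-varying value. The same section adds that "PSA levels will be assessed according to the schedule described by the study calendar above and PSA doubling time will be calculated". The Study Calendar has six PSA draws: screening, Day 0, Day 30, Day 90, and 6 months and 1 year after HCQ ends.

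No section defines a PFS that leaves out PSA-only events.

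**The concern.** There are two linked problems.

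The first is the label. Median PFS is a named secondary endpoint. Reported under the wording of 1.2, it would be read as time to symptomatic or radiographic worsening, when a laboratory value alone can end it.

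The second is overlap between outcome and covariate. The PSA event is a rise from baseline. A covariate that measures PSA rise from baseline partly measures the event, so the model could present PSA kinetics as prognostic for progression when it has mostly recovered the event definition. Correct timing of the covariate, for example a Day-90 landmark, does not remove this: a man already closer to the PSA threshold at the landmark will tend to cross it sooner.

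**Working it through.** **The plan's own figure.** None is stated for PFS or the Cox model. The only design calculation (13.1.2, primary endpoint) reproduces: Φ((√18 × 0.30 − 1.96 × √(0.20 × 0.80)) / √(0.50 × 0.50)) = Φ((1.273 − 0.784)/0.5) = Φ(0.978) = 83.6%, stated as 84%; and 18/0.9 = 20. It has no bearing on this point.

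**Step 1: how PSA kinetics set the event time.** Use the 11.3 rule, to which 11.4.2 refers back, and read 2 ng/mL as an absolute rise. Assume exponential PSA growth from enrolment with doubling time DT. The threshold is reached at t = DT × log2(1 + required proportional rise).

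| Baseline PSA (ng/mL) | Required rise | t, DT 6 months | t, DT 12 | t, DT 24 |
|---|---|---|---|---|
| 1.9 | 25% | 1.9 | 3.9 | 7.7 |
| 2 | 2/2 = 100% | 6.0 | 12.0 | 24.0 |
| 4 | 2/4 = 50% | 3.5 | 7.0 | 14.0 |
| 8 or more | 25% | 1.9 | 3.9 | 7.7 |

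For a given baseline, the PSA event time is a constant times DT. Doubling time, or 3-month change (3/DT doublings), is therefore tied to the outcome. Baseline PSA enters only through the threshold, and not in one direction.

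**Step 2: simulation.** Non-PSA events were generated independently of PSA, so a valid test should reject in about 5% of trials. None of the inputs below is in the documents, apart from the PSA rule and the approximate draw times.

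- Simulation A: 20 men; median baseline PSA 1, 3 or 8 ng/mL (log SD 1); median doubling time 6, 12 or 24 months (log SD 0.7), with PSA rising from enrolment; median time to a non-PSA event 18 months; 36 months' follow-up; draws at about months 1, 3, 9 and 15; 1,500-2,000 trials per scenario.
- Simulation B: 18 men; Day-90 landmark; median Day-90/Day-0 PSA ratio 0.4-0.6 (log SD 0.4-0.8); median doubling time 6-8 months; median clinical PFS 12-24 months; censoring 33 months after the landmark; 800 trials per scenario.
- Simulations C and D: two further checks, each with 18 men, a Day-90 landmark and other assumed inputs.

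Share of trials rejecting at 5% when a PSA rise counts as an event (11.3 rule):

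| PSA covariate | A | B | C | D |
|---|---|---|---|---|
| Time-varying change | 81-97% | | | |
| Doubling time | 55-93% | | | |
| 3-month change or Day-90/Day-0 ratio | 53-90% | 43-69% | 24-53% | 18-51% |
| 3-month or Day-90 level | 5-38% | | 8-23% | 5-17% (log), 10-24% (untransformed) |
| Current level | 5-26% | | | |
| Baseline | 4-15% | | 5-6% | 3-6% |

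With PSA-only events dropped, rejection was about 5-7% in A, B and C. In B the spurious hazard ratio had a median of 2.2 to 4.1 per PSA doubling. A separate run with baseline log PSA alone gave 6%. Monte Carlo standard error with 800 trials is √(0.5 × 0.5/800) = 1.8 percentage points at 50% and √(0.05 × 0.95/800) = 0.8 points at 5%.

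**Step 3: how often PSA comes first.** In A, PSA rise was the first event in about 45-82% of patients; in B, in 51-75% of events.

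**Step 4: sensitivity to the PSA wording.** The documents define PSA progression in three ways. Section 11.3 has a separate branch (25% alone) for men below "2 ng/mL at study enrollment"; the list in 11.4.2 omits it; section 5.5 has "PSA progression (an increase in PSA > 25% above baseline at study entry", with no absolute minimum. Rerunning A at doubling times of 6 and 24 months:

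| Rule | Time-varying change | Doubling time | Baseline |
|---|---|---|---|
| 11.4.2 read literally (no PSA event if baseline is below 2) | 7-65% | 7-67% | 10-74% |
| 5.5 | 98-100% | 77-97% | about 5% |

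The size of the artefact, and which covariate carries it, thus depends on which wording is applied.

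**The case against.** A reader might infer that a PSA-PFS association is guaranteed by definition. The documents do not support that. Section 13.3.2 speaks of PSA levels and names no form. For baseline PSA under the 11.3 rule the artefact is mostly negligible, and for a raw post-baseline level it is weak to moderate. This part of the objection stands. The ambiguity does not clear the plan, though: serial draws are scheduled, doubling time will be calculated, and nothing excludes the circular forms.

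The analysis is labelled exploratory, in a single arm of 20 men. No test level, sample size or decision depends on it, and the primary endpoint is PAR-4. This stands and limits the consequence; the rejection rates measure the artefact, not a decision error that the plan would make.

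The label could be called editorial, since 11.4.2 lists all four events openly. That is fair for someone who reads the definition. It does not help a reader who sees only a median reported under the wording of 1.2.

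A reader might also infer that the median will be mostly a time to PSA rise. That depends wholly on the assumed PSA distribution and clinical event rate.

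Finally, a PSA-free PFS needs more than an extra curve. Section 11.4.2 dates only the first event, and no section requires progression to be dated and typed after a PSA-only event. This stands and is built into the fix.

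**Conclusion.** The concern holds in a conditional form. The label is wrong as written, whatever covariate is chosen. The circularity is material if PSA enters as on-study change, ratio or doubling time: about 24-90% rejection for 3-month change or ratio (one check went down to 18%) and 55-93% for doubling time. These percentages assume the 11.3 event rule, clinical events unrelated to PSA, and the PSA and event distributions listed above; they show direction and rough size and are not forecasts for this trial.

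ADT-free survival, regressed on PSA in the same sentence, does not count PSA as an event. It keeps a softer link, because 11.4.1 allows ADT to be considered at PSA progression. A PSA-free PFS keeps one too, because Study Calendar note 6c lets a rising PSA trigger imaging; in Simulation D that residual was small (6-9% rejection).

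The point merits a change to the plan but does not threaten its main conclusion.

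**What to change.** 1. Relabel the composite *PFS including PSA progression* in 1.2 and 11.4.2.
2. Add *clinical PFS*: first symptomatic, local or distant progression, or death, with PSA-only events not counted. Report its Kaplan-Meier median beside that of the composite, and use it in every model that has post-baseline PSA as a covariate.
3. In 13.3.2, name the PSA covariate and its timepoint. If it is post-baseline, specify a landmark or time-dependent model.
4. Record the date and type of non-PSA progression after a PSA-only event, and state how ADT started in between is handled in the analysis. Without these dates, clinical PFS could only be censored at the PSA rise, and that censoring would be informative.
5. State as limitations that PSA progression may prompt ADT (11.4.1) and imaging (Study Calendar note 6c).
6. Reconcile the PSA-progression wording in 5.5, 11.3 and 11.4.2.

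Cost: wording changes, one more Kaplan-Meier curve and a small amount of added data recording. Clinical PFS will have fewer events and a wider interval than the composite.
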